- Overall response rate (CR or PR) will be calculated with 95% CI for each disease-specific cohort (B1, B2, B3, and B4) on the response-evaluable population.
- Progression-free survival and overall survival at 1 year will be evaluated using Kaplan-Meier method.
- Duration of response and duration of stable disease will be evaluated if there are sufficient data for responders within each cohort.

Table 1: Time and Events Schedule

| | Notes | Screening Period | Treatment Period (14 day cycles) | | | Follow-up Period ^a |
|---|--|---|---|--------------------------|-----|-------------------------------|
| | | up to 28 days before start of any study treatment | BASELINE ASSESSMENT CID1 (without run-in phase) CID-7 (with run-in phase) | Day 1, subsequent cycles | EOT | Q3m |
| 
Treatment Period begins with the first administration of study therapy. EOT visit is required for all subjects and should take place within 30 days after last dose of study therapy with a window of ± 7 days. If the subject requires subsequent anti-lymphoma/neoplastic therapy in the interim period between last dose of study drug and the EOT visit, then this visit should be completed just prior to initiation of subsequent therapy. Follow-up visits in all subjects will be completed every 3 months with a window of ± 7 days until death or end of study. Note that the first FU visit should be approximately 100 days after end of nivolumab therapy; during this first FU visit, additional sampling will be done.
 
After the clinical cutoff, subjects who are ongoing on treatment continue all assessment per protocol, however data collected on eCRF will be limited to at least: SAEs and AEs Grade ≥ 3, laboratory assessments (Grade ≥ 3 or clinically significant), efficacy assessments, survival status, and study treatment administration.
 
Per Amendment 7, subjects who are receiving study treatment will continue all assessments per protocol. Data collected in the eCRF will be further limited to: SAEs and Grade ≥ 3 AEs that are at least possibly related to treatment, AEs leading to discontinuation or modification, efficacy assessments, and study treatment administration.
 | | | | | | |
| Screening/Administrative | | | | | | |
| Informed consent | ICF must be signed before any study-related procedures are performed. | X | | | | |
| Eligibility criteria | | X | | | | |
| Demography/ Medical History | | X | | | | |
| Study Drug Administration | | | | | | |

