| | Grade 2 | 
1st event: Hold until resolution to Grade ≤ 1.
 
 Improvement to \leq Grade 1: Resume study therapy at same dose and schedule. Worsening or persistence >3 days from day of onset despite oral steroid treatment: discontinue study therapy. 
2nd event: discontinue study therapy
 |
| | Grade 3 and 4 | Discontinue study therapy. |
| Renal/Creatinine | Section 8.5. (Table 14): Management of Renal Adverse Events | |
| | Grade 1 | Continue study therapy. |
| | Grade 2 and 3 | 
1st event: Hold until resolution to Grade ≤ 1.
 
 Improvement to \leq Grade 1: Resume study therapy at same dose and schedule. Worsening or persistence >7 days from day of onset: Discontinue study therapy. 
2nd event: discontinue study therapy
 |
| | Grade 4 | Discontinue study therapy. |
| Pneumonitis | Section 8.7. (Table 16): Management of Pulmonary Adverse Events | |
| | Grade 1 | 
Consider holding study therapy.
 
Improvement to baseline: resume dosing.
 
Worsening or persistence >7 days from day of onset: hold study therapy and treat as Grade 2.
 |
| | Grade 2 | 
Hold study therapy until resolution to Grade ≤ 1
 
Improvement to Grade ≤ 1 within 2 weeks: resume dosing.
 
Persistence for >2 weeks from day of onset: Discontinue study therapy.
 |
| | Grade 3 and 4 | Discontinue study therapy. |
| Hepatic alteration | Section 8.2. (Table 11): Management of Hepatic Adverse Events | |
| | Grade 1 | 
Continue study therapy.
 
Worsening or persistence >7 days from day of onset: hold study therapy and treat as Grade 2.
 |
| | Grade 2 | 
Hold study therapy until resolution to Grade ≤ 1.
 
Improvement to Grade ≤ 1 within 2 weeks: resume at same dose and schedule.
 
Persistence for >2 weeks from day of onset: Discontinue study therapy.
 |
| | Grade 3 and 4 | Discontinue study therapy. |
| AST/ALT and Bilirubin | Section 8.2. (Table 11): Management of Hepatic Adverse Events | |
| | Grade 1 | Continue study therapy. If worsens treat as Grade 3. |
| | Grade 2 | 
Consider hold study treatment until resolution to Grade ≤ 1
 
Persistent^a ≤ 12 weeks: Continue therapy at same dose and schedule.
 
Persistent^a >12 weeks: Discontinue study therapy
 |
| | Grade 3 and 4 | Discontinue study therapy |
| Recommendations for the management of immune-related adverse events and adverse events of clinical interest are provided in Section 8. | | |

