8.1. Gastrointestinal AE

Diarrhea and colitis have been observed in subjects receiving nivolumab. Early recognition and treatment of diarrhea and colitis are critical to their management. Subjects should be advised to seek immediate medical evaluation if they develop new-onset diarrhea, blood in stool, or severe abdominal pain or if they have worsening of baseline diarrhea. In subjects with pre-existing diverticulosis and/or diverticulitis receiving concomitant medication with corticosteroids, non-steroidal anti-inflammatory drugs (NSAIDs), and opioid analgesics together with nivolumab, diverticular perforation has been observed.

Table 10: Management of Immune-related Gastrointestinal Adverse Events

| Management and Follow-up of Immune-related Gastrointestinal Adverse Events. For dose modification guidelines, refer to Table 8 and Table 9. | |
|--|--|
| Grade 1 | Symptomatic treatment according to institutional standards Close monitoring; instruct subject to report worsening immediately and treat as Grade ≥ 2 |
| Grade 2 | ≤ 5 days: Symptomatic treatment according to institutional standards >5 days or recurrence: 0.5–1.0 mg/kg/d methylprednisolone.; consider prophylactic antibiotics; Persistence or worsening despite steroids >3 days: treat as Grade 3/4 Improvement to \leq Grade 1: taper steroids over at least 1 month, consider prophylactic antibiotics for opportunistic infections, resume study therapy per protocol |
| Grade 3-4 | Immediately: 1.0–2.0 mg/kg/d methylprednisolone IV; consider prophylactic antibiotics and lower endoscopy Persistence >3 days or recurrence: add infliximab 5 mg/kg (if no contraindication such as perforation or sepsis) Improvement to \leqGrade 2 within ≤ 3 days: taper steroids over at least 1 month |
| General | The oral corticosteroid equivalent of the recommended IV dose may be considered for ambulatory patients; the lower bioavailability of oral corticosteroids need to be considered. Clinical caution should be exercised, for subjects receiving concomitant medications of corticosteroids, NSAID, or opioid analgesics. In addition, be vigilant for signs and symptoms of potential perforation, especially in subjects with known diverticular disease. Narcotics should be used with caution as pain medicines may mask the signs of colonic perforation. |

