8.5. Renal Adverse Events

Elevated creatinine and biopsy-confirmed tubulointerstitial nephritis and allergic nephritis have been infrequently observed following treatment with nivolumab. Physicians should monitor creatinine regularly.

Table 14: Management of Renal Adverse Events

| Management and Follow-up of Renal Adverse Events. For dose modification guidelines, refer to Table 8 and Table 9. | |
|--|---|
| Grade 1 | Monitor creatinine weekly Creatinine returns to baseline: continue monitoring per protocol Creatinine increases: treat as Grade ≥ 2 |
| Grade 2-3 | Monitor creatinine every ≤ 3 days Immediately: start 0.5-1.0 mg/kg/d methylprednisolone IV or oral equivalent; consider prophylactic antibiotics; consider renal biopsy Improvement to \leq Grade 1: taper steroids over at least 1 month Persistence > 7 days or worsening: treat as Grade 4 |
| Grade 4 | Monitor creatinine daily Immediately: consult nephrologist; consider renal biopsy; start 1.0-2.0 mg/kg/d methylprednisolone IV or IV equivalent; add prophylactic antibiotics Improvement to \leq Grade 1: taper steroids over at least 1 month |
| General | Patients on IV steroids may be switched to an equivalent dose of oral corticosteroids (eg, prednisone) at start of tapering or earlier, once sustained clinical improvement is observed. The lower bioavailability of oral corticosteroids need to be considered |

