12.2. Safety Analyses

Adverse Events

The verbatim terms used in the eCRF by investigators to identify AEs will be coded using the most current version of the Medical Dictionary for Regulatory Activities (MedDRA). Toxicities will be graded for severity according to NCI-CTCAE, version 4. All reported AEs with onset during the Treatment Period (ie, treatment-emergent adverse events [TEAEs], and AEs that have worsened since baseline) will be included in the analysis.

Specifically, the following will be summarized:

- Incidence of DLT (Part A)
- All adverse events
- Grade 3 or higher adverse events
- Serious adverse events
- Adverse events leading to discontinuation of treatment

- Adverse events leading to death
- Adverse events of special interest

Summaries, listings, datasets, or subject narratives may be provided, as appropriate, for those subjects who die, who discontinue treatment due to an adverse event, or who experience a severe or a SAE.

Clinical Laboratory Tests

Laboratory data will be summarized by type of laboratory test. Reference ranges and markedly abnormal results (specified in the Statistical Analysis Plan) will be used in the summary of laboratory data. Descriptive statistics will be calculated for each laboratory analyte at baseline. Parameters with predefined toxicity grades will be summarized. Change from baseline to the worst grade experienced by the subject during the study will be provided as shift tables.

Vital Signs

Descriptive statistics of heart rate and blood pressure (systolic and diastolic) (supine) values and changes from baseline will be summarized. The percentage of subjects with clinically important changes from baseline will be summarized.

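### Table 9's 3-day stopping limit for a first Grade 2 diarrhoea runs from onset, so it has expired before Table 10 starts the steroid it is meant to test

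*Protocol*

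**What the plan says.** Protocol Section 6.4.3, Table 9, row for enterocolitis or diarrhoea, Grade 2, first event: hold both drugs until the event is back to Grade 1 or better, then resume at the same dose. The stopping rule is "Worsening or persistence >3 days from day of onset despite oral steroid treatment: discontinue study therapy". A second event means discontinuation. The row refers the reader to Section 8.1, Table 10.

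Table 10, Grade 2, sets this sequence:

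- Up to 5 days: symptomatic treatment only.
- Steroid start: ">5 days or recurrence: 0.5–1.0 mg/kg/d methylprednisolone".
- Steroid failure: "Persistence or worsening despite steroids >3 days: treat as Grade 3/4". Table 9 discontinues at Grade 3 and 4.
- On improvement to Grade 1 or better: "taper steroids over at least 1 month, consider prophylactic antibiotics for opportunistic infections, resume study therapy per protocol".
- Route, from the General row: "The oral corticosteroid equivalent of the recommended IV dose may be considered for ambulatory patients".

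Section 6.4 notes that a recommendation to discontinue applies to both drugs. Ibrutinib alone was possible after consulting the sponsor. Since Amendment 7 it is limited to subjects rolling over to the extension study.

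**The concern.** The two tables are meant to be used together on the same event, but they count 3 days from different starting points. Table 9 counts from onset of the diarrhoea; Table 10 counts from the start of steroid. Because Table 10 delays the steroid beyond 5 days, Table 9's time condition is already satisfied when the first steroid dose is given. A site reading Table 9 literally can regard both of its conditions as met at that moment and stop both drugs. A site working from Table 10 would give the steroid its 3 days and resume study therapy if the subject improves.

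Two sites treating the same event identically can therefore disagree on permanent discontinuation. The consequences are possible loss of therapy in a steroid-responsive subject and inconsistent counting of discontinuations. Those counts matter because Section 12.2 plans a summary of "Adverse events leading to discontinuation of treatment". Table 1 also keeps, under Amendment 7, a reduced data set that still includes "AEs leading to discontinuation or modification, efficacy assessments, and study treatment administration".

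**Working it through.** No sample size or error rate is involved. The check is a day count, with onset as Day 1.

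**Inputs**

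- Table 9 time limit: more than 3 days from onset, reached on Day 4.
- Table 10 steroid start: more than 5 days from onset, so Day 6.
- Table 10 steroid failure: more than 3 days on steroid, so 3 days after the start day.

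**Table 10 followed as written**

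- Table 9 has two joined conditions, and persistence despite steroid cannot be claimed before the steroid starts. The first day on which both can be called met is max(4, 6) = Day 6.
- Steroid failure under Table 10 falls on 6 + 3 = Day 9.
- Spread: 9 − 6 = 3 days.

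**Steroid started earlier**

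Table 10 leaves the first 5 days to institutional standards and does not bar an earlier steroid. For a start on Day d, the spread is (d + 3) − max(4, d):

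| Steroid start, Day d | Table 9 can be called met, max(4, d) | Steroid failure, d + 3 | Spread (days) |
|---|---|---|---|
| 1 | 4 | 4 | 0 |
| 2 | 4 | 5 | 1 |
| 3 | 4 | 6 | 2 |
| 4 | 4 | 7 | 3 |
| 5 | 5 | 8 | 3 |
| 6 | 6 | 9 | 3 |

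Comparing the bare limits, without requiring the steroid to have started, gives a wider gap: more than 3 days against more than 5 + 3 = 8 days from onset, or 5 days. The 3-day figure is the more cautious one.

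**Who can use Table 10's resume path**

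With Table 10 timing, a first event that reaches the steroid step is already past Table 9's limit. Table 10's other steroid trigger is recurrence; read as a second event, Table 9 discontinues it outright. On the literal reading, nobody is left to improve on steroid and resume.

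**Comparison with other Table 9 rows that count from onset**

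| Event | Table 9 limit from onset | Steroid start in the management table | Time for a steroid trial? |
|---|---|---|---|
| Renal, Grade 2–3 | >7 days | At once (Table 14) | Yes |
| Pneumonitis, Grade 2 | >2 weeks | At once (Table 16) | Yes |
| Hepatic alteration, Grade 2 | >2 weeks | After >5 days (Table 11) | Yes |
| Diarrhoea, Grade 2, first event | >3 days | After >5 days (Table 10) | No |

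Table 14 says "Immediately: start 0.5-1.0 mg/kg/d methylprednisolone IV or oral equivalent" and escalates at the same 7-day point that Table 9 uses, so an onset count works there. Only the diarrhoea row pairs a delayed steroid with a limit that expires first.

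**The case against.** The strongest reply is that any clinician will read the row as failure of a steroid trial. Table 9 cannot stop an untreated subject, and calling diarrhoea persistent despite a steroid on the day it is first given is strained. Table 10 uses the same number, 3 days, for failure on steroid. That reading is probably what was intended. It is not what the row says, though: the renal, pneumonitis, hepatic and uveitis rows use the same onset phrase to mean onset of the event.

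A second reply is that Table 10 governs medical management and defers to Tables 8 and 9 for dosing, so its resume line creates no separate rule. Table 9 itself allows resumption on improvement. This is fair as to which table controls. It does not help, because the controlling table holds the limit that expires first. It is also true that Day 9 as a discontinuation day is an inference, from Table 10's escalation to Grade 3/4 management combined with Table 9's rule for those grades.

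Third, Table 10's Grade 2 line names no route, so Table 9's mention of oral steroid is not a flat contradiction. That stands. The General row nevertheless treats the oral form as an option, and the narrower word in Table 9 leaves a subject on IV steroid uncovered.

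Fourth, the effect is small. Non-responders are discontinued either way, dosing is held either way, and a held subject may still be recorded under dose modification. The SAP (Section 5.1) also tabulates events by action taken. All of this stands and limits the size of the problem.

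**Conclusion.** The concern holds. As written, Table 9 can end both drugs in a first Grade 2 diarrhoea event before the steroid has been tried, contrary to Table 10's provision for subjects who improve on steroid.

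With Table 10's timing the disagreement is 3 days (Day 6 against Day 9). It ranges from 0 to 3 days for steroid starts on Days 1 to 6. This assumes onset is Day 1, that the despite-steroid condition needs the steroid to have started, and that escalation to Grade 3/4 management carries Table 9's discontinuation with it.

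The readings lead to different outcomes only for subjects who are still at Grade 2 when the onset limit is met with steroid started, and who then improve within the 3-day steroid window. The documents give no rate for persistent Grade 2 diarrhoea, so their number is unknown. There is no added drug exposure, and no efficacy analysis is shown to change. Section 3.3.1 ties Table 9 discontinuations to the DLT definition, but Part A dose decisions are past and are not affected. The row still governs subjects on treatment, and it should be corrected.

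**What to change.** In Table 9, enterocolitis or diarrhoea, Grade 2, first event, replace the limit with: *Worsening, or persistence >3 days after start of steroid treatment: discontinue study therapy.* This matches Table 10's failure rule. Say steroid rather than oral steroid, so that either route is covered.

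The cost is a wording change in one table row, with no new visits or assessments. Subjects whose diarrhoea does not respond to steroid would stay on hold, not dosed, for up to about 3 more days before discontinuation.

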3.3.1. Evaluation of Dose-limiting Toxicity

Dose-limiting toxicities will be assessed during the first and second treatment cycle (ie, first 28 days of study therapy) starting with the first day of combination therapy (ibrutinib and nivolumab). Only AEs that occur during this time period, and after a subject has received at least one dose of nivolumab and one dose of ibrutinib, will be considered for DLT. Adverse events fulfilling the criteria of DLT need to be reviewed and confirmed by the SET. In addition, all AEs occurring while a subject is participating in the study will be reviewed by the SET as part of the continued safety evaluation ([Section 12.7](#)). All subjects in Part A will be evaluated for DLTs. Subjects who are not evaluable for DLT may be replaced; the safety profile of subjects who were replaced will be included in the SET review.

The following AEs considered to have at least a possible relationship to study therapy by the investigators and confirmed by the SET will qualify as DLTs:

- Any AE that requires discontinuation of study drug (see also Section 6.4.3, Table 8, and Table 9)
- Any AE that results in a delay of dosing for more than 2 weeks within the DLT period
- Central nervous system hemorrhage of any grade.

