| Adverse Event | CTCAE Grade | Ibrutinib and Nivolumab |
| Endocrinopathy | Section 8.3. (Table 12): Management of Endocrinopathies | |
| | Asymptomatic | Continue study therapy. |
| | Symptomatic | Abnormal lab values and pituitary MRI scan: Hold study therapy until improvement to Grade ≤ 1 ; resume at same dose and schedule. |

Table 8: Dose Adjustments for Related Non-hematologic and Related Hematologic Toxicities

| | | |
|-------------------------------------|---|---|
| | Suspicion of adrenal crisis | Hold study therapy; discontinue study therapy if no improvement after adrenal hormone replacement. |
| Rash | Section 8.4. (Table 13): Management of Rash | |
| | Grade 1 | Continue study therapy. |
| | Grade 2 | Persistent ^a ≤12 weeks: Continue therapy at same dose and schedule. Persistent ^a >12 weeks: Discontinue study therapy |
| | Grade 3 | Hold study therapy until resolution to ≤ Grade 1 Persistent >2 weeks or inability to reduce steroid ≤10 mg/day >12 weeks: Discontinue study therapy. Discontinue if Grade 3 rash recurs. |
| | Grade 4 | Discontinue study therapy |
| Neurological | Section 8.6. (Table 15): Management of Neurological Adverse Events | |
| | Grade 1 | Continue study therapy. |
| | Grade 2 | Hold study therapy until improvement to Grade ≤1; then resume study therapy. |
| | Grade 3 and 4 | Discontinue study therapy. |
| Uveitis or visual complaints | Section 8.8. (Table 17): Management of Uveitis and Visual Complaints | |
| | Grade 1 | Consider hold study therapy. |
| | Grade 2 | Hold study therapy until improvement to Grade ≤1; then resume study therapy. Persistence for >2 weeks from day of onset despite symptomatic treatment: Discontinue study therapy. |
| | Grade 3 and 4 | Discontinue study therapy. |

- a. Persistent treatment-related adverse event that do not recover to Grade ≤1 within 12 weeks after last dose of nivolumab.

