8.2. Hepatic Adverse Events

Hepatic AEs, including elevated liver function tests (LFTs) and, infrequently, drug-induced-liver-injuries (DILI) have been observed following treatment with nivolumab. Early recognition and treatment of elevated LFTs and DILI are critical to their management. Subjects should be advised to seek medical evaluation if they notice jaundice (yellow appearance of skin or sclera) or if they develop bruising, bleeding, or right-sided abdominal pain. Physicians should monitor LFTs prior to each nivolumab treatment.

Table 11: Management of Immune-related Hepatic Adverse Events

| Management and Follow-up of Immune-related Hepatic Adverse Events. For dose modification guidelines, refer to Table 8 and Table 9. | |
|---|---|
| Grade 1 | Monitor LFTs as outlined in the protocol; Worsening: treat as Grade ≥ 2 |
| Grade 2 | Monitor every 3 days; Returning to baseline: resume per protocol monitoring LFT elevation >5 days or worsening: 0.5 – 1.0 mg/kg/d methylprednisolone IV or oral equivalent; consider prophylactic antibiotics LFT return to \leqGrade 1 or baseline: taper steroids over at least 1 month; resume routine monitoring and resume study treatment per protocol |
| Grade 3-4 | Monitor every ≤ 2 days; Immediately: 1. –2.0 mg/kg/d methylprednisolone IV or IV equivalent; start prophylactic antibiotics; consult gastroenterologist Persistence >3 days or recurrence: add mycophenolate mofetil 1g bid; if no response within ≤ 5 days consider other immunosuppressants per local guidelines LFT return to Grade 2: stop immunosuppressants LFT return to \leqGrade 1: taper steroids over at least 1 month |

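### Table 9's AST/ALT and Bilirubin row gives opposite orders for the same Grade 2 rise, and no written rule says which row governs a raised liver test

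*Protocol*

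**What the plan says.** Table 9 in Protocol Section 6.4.3 has two adjacent liver rows, and both point to Section 8.2 and its Table 11.

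- *AST/ALT and Bilirubin*, Grade 1: "Continue study therapy. If worsens treat as Grade 3". Grade 2: "Consider hold study treatment until resolution to Grade" 1 or lower, then continue if the event persists up to 12 weeks and discontinue beyond that. Footnote a defines persistence as failure to recover "within 12 weeks after last dose of nivolumab". Grades 3 and 4: discontinue.
- *Hepatic alteration*, Grade 1: continue, with the rider "Worsening or persistence >7 days from day of onset: hold study therapy and treat as Grade 2". Grade 2: a mandatory hold, resumption on recovery within 2 weeks, otherwise "Persistence for >2 weeks from day of onset: Discontinue study therapy". Grades 3 and 4: discontinue.

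The term hepatic alteration is not defined. Section 8.2 opens by counting raised liver tests as hepatic events: "Hepatic AEs, including elevated liver function tests (LFTs". Table 11 says a worsening Grade 1 is to be treated as Grade 2 or higher, but for dosing its header states: "For dose modification guidelines, refer to Table 8 and Table 9".

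Table 8 has a third candidate, the *Lab values* row: continue at Grade 1; continue at Grade 2 for up to 12 weeks; hold at a first Grade 3; discontinue at a second Grade 3 or at Grade 4. Section 6.4.3 gives general toxicities to Table 8, and immune-related events and other events of clinical interest to Table 9.

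Section 3.3.1 makes an AE a DLT if it is at least possibly related, is confirmed by the SET, and requires discontinuation under Table 8 or 9. A dosing delay of more than 2 weeks within the DLT period is a separate route to a DLT.

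**The concern.** A dose-modification table should give one order for one clinical state. Here the AST/ALT and Bilirubin row gives two for Grade 2, and the harsher one falls on the subject who started milder. An investigator who turns to Table 11 or to the neighbouring row finds a different instruction again.

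This would be only a drafting matter if the tables did not also define an endpoint. They do. Through Section 3.3.1, an order to discontinue is the criterion for a DLT, and the Amendment 2 summary confirms the sponsor's view that revising these tables changes what qualifies. At stake are the reported Part A DLT incidence (Section 12.2) and the management of subjects still on treatment. Under the Amendment 7 note in Table 1, those subjects continue all assessments, and chemistry is reviewed before each nivolumab infusion.

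**Working it through.** The plan gives no figure to reproduce. The check sets the orders side by side and then looks at timing.

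**1. The AST/ALT and Bilirubin row alone.** A rise from Grade 1 straight to Grade 3 or 4 is already covered by the Grade 3-4 line. The worsening clause therefore adds something only when the rise stops short of Grade 3, which in practice means Grade 2. There it orders discontinuation, while the Grade 2 line makes a hold optional and allows dosing to continue. The two lines contradict each other.

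**2. Against Table 11.** Table 11 sends a worsening Grade 1 to Grade 2 or above, and its Grade 2 entry allows treatment to resume once the test has recovered. Table 9's jump to Grade 3 rules that out.

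**3. Across the three candidate rows.**

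| Course | AST/ALT and Bilirubin | Hepatic alteration | Table 8 Lab values |
|---|---|---|---|
| Grade 1 rising to Grade 2 | Discontinue | Hold, manage as Grade 2 | Continue, 12-week limit |
| Grade 1 unchanged beyond 7 days | Continue | Hold, manage as Grade 2 | Continue, monitor closely |
| Grade 2 at first detection, lasting 15 days | Hold optional, may continue | Discontinue | Continue, 12-week limit |
| First Grade 3 | Discontinue | Discontinue | Hold, resume on recovery |
| Grade 4 | Discontinue | Discontinue | Discontinue |

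The two Table 9 rows agree at Grades 3-4 and differ at Grades 1-2. Neither is uniformly the cautious choice: the AST/ALT row is stricter on worsening, the Hepatic row on persistence.

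**4. A dated example inside the DLT window.** The window is 2 cycles × 14 days = 28 days. Chemistry is drawn within 48 hours before each cycle. Cycle 2 Day 1 is Day 15, so that sample falls on Day 13-15. Cycle 3 Day 1 is Day 29, so that sample falls on Day 27-29. Take Grade 1 on the first sample and Grade 2 on Day 27 or 28. The AST/ALT row orders discontinuation, which is a DLT if the event is related and SET-confirmed. The Hepatic row orders a hold.

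**5. Timing of the persistence limits.** Section 3.3.1 requires the AE to occur in the window; it does not say that the discontinuation trigger must also fall there. *If* one assumes the trigger must fall by Day 28:

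- Hepatic row: more than 14 days after onset on day d is first met on day d + 15. Then d + 15 ≤ 28 gives d ≤ 13.
- AST/ALT row: 12 × 7 = 84 days after the last nivolumab dose, so the earliest is Day 1 + 84 = Day 85, which is outside the window.

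Without that assumption these limits do not apply.

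**The case against.** The best defence is that one row names AST, ALT and bilirubin, so those tests belong there. Section 8.2 mentions drug-induced liver injury alongside raised tests, which gives the Hepatic alteration row a plausible separate purpose. Table 9 is also headed as covering immune-related events, so a related rise not judged immune-related may fall under Table 8, where there is no worsening clause. The SET confirms every DLT. And on the Day 28 assumption the persistence difference is nearly empty: of the scheduled pre-Cycle 2 sampling days (13-15), only Day 13 meets the limit.

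Much of this stands. Sending the named tests to the named row is the natural reading, so the overlap between rows is the softer half of the point. But that reading is unwritten, and adopting it leaves the contradiction inside the named row untouched. Table 8 narrows the affected events without removing them, because Section 6.4.3 also sends events of clinical interest to Table 9 and Section 13.2.1 lists hepatic events among those for nivolumab. SET confirmation gives central judgement but no written tie-break.

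Three stronger readings are tempting, and the documents do not support them.

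- A reader might count the Grade 1-2 differences and say that exactly two of the three can change DLT status. The third, Grade 1 beyond 7 days, leads in the Hepatic row to management as Grade 2 and from there possibly to discontinuation, or to a hold long enough to be a DLT by delay. No clean tally follows.
- A reader might infer that the recommended dose is unsafe or wrong, since in Attachment 1 with 6 subjects 1 DLT means escalate, 2 stay and 3 de-escalate. One reclassified event could move such a decision in principle, but no Grade 1-2 liver-test event is reported.
- A reader might question the reported Grade 3 bilirubin DLT because Table 8 would only hold at a first Grade 3. Its recorded status matches both Table 9 liver rows, and nothing in the documents reopens it.

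**Conclusion.** The point holds as a minor one. The AST/ALT and Bilirubin row contradicts itself at Grade 2 and departs from Table 11 and from the adjacent row. The scopes of the two Table 9 liver rows and of Table 8's Lab values row are not stated. For some related Grade 1-2 courses the row used decides whether a DLT is counted, unless dosing is delayed more than 2 weeks within the DLT period, which is a DLT either way.

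The internal contradiction rests on the text alone and is firm. The overlap is less firm, because a natural though unwritten reading exists. The consequence is a possibility only: the number of affected subjects is unknown and may be zero of up to 18. Dose finding is finished, so what remains is the transparency of the Part A DLT incidence and clear instructions for subjects still treated.

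**What to change.** Reword the AST/ALT and Bilirubin Grade 1 line so that a worsening event is managed according to the grade it reaches, which fits both that row's Grade 2 line and Table 11. The word Grade 3 may be a slip for Grade 2, but the documents do not say so, and the clinical choice is the sponsor's. Then state which events each Table 9 liver row and the Table 8 Lab values row cover, or merge the two liver rows.

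In the study report, state which row the SET applied to Part A liver-test events and list any event whose DLT status depends on that choice. The report is the right place, since the addendum covers data collected after the primary analysis. DLTs should not be redefined with a newly chosen limit.

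The cost is minor wording changes, a disclosure sentence, and a short review of existing liver tests in up to 18 subjects. No new data are needed.
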